2. BRIEF SUMMARY

The purpose of this study is to assess the safety and efficacy of a newly developed psychotherapy for schizotypal personality disorder. This new form of psychotherapy integrates compassion focused therapy and metacognitively oriented psychotherapy.

3. SYNOPSIS

Trial Title	Compassion and Metacognition Based Therapy for Schizotypal Personality Disorder: A Pilot Non-inferiority Randomized Controlled Trial on Repeated Measures.
Internal ref. no. (or short title)	Compassion and Metacognition in Schizotypal Personality (CMBT).
Trial registration	Unique Protocol ID: 03-07072020
Sponsor	Tages Onlus [name]
Funder	N/A
Clinical Phase	Recruiting
Trial Design	Parallel Assignment Randomized Controlled Trial with Repeated Measures
Trial Participants	Minimum Age: 18 Years Being diagnosed with Schizotypal Personality Disorder at SCID-5-AMPD
Sample Size	14
Planned Trial Period	Total lenght: December 15, 2020 - December 20, 2021

	Pre-post evaluation between pre-assessment (1-month before the intervention) and 1 month follow-up.		
Planned Recruitment period	December 15, 2020 - September 30, 2021		
	Objectives	Outcome Measures	Timepoint(s)
Primary		Personality pathology: Total score at PID-5-BF	(i) at 1 month before intervention starts; (ii) once the treatment starts; (iii) 6 measurements at the end of each month of intervention; at 1-month follow-up.
Secondary		Schizotypal Personality Disorder Diagnosis: Diagnosis at the 3rd module of SCID-5-PD interview; General Psychopathology: Total score at SCL-90-R; Metacognition: Total score at MAS-A	Pre-post evaluation between pre-assessment (1-month before the intervention) and 1-month follow-up assessment.
Intervention(s)	
 IMP(s) nIMP(s) Other intervention(s) 	Compassion and Metacognition Based Therapy (CMBT): Third Wave Cognitive Therapy targeting metacognitive dysfunctions (through Metacognitively Oriented Psychotherapy) and selfcriticism (through Compassion Focused Therapy). 6-month therapy, including 24 weekly sessions.	
Comparator	Cognitive Behavioral Therapy: Standard Cognitive Behavioral Therapy for Personality Disorders plus Standard Psychopharmacological Treatment. 6-month therapy, including 24 weekly sessions.		

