6. OBJECTIVES AND OUTCOME MEASURES

Objectives	Outcome Measures	Timepoint(s) of evaluation of this outcome measure (if applicable)
Primary Objective To compare the effect of the CMBT-S versus CBT plus standard psychopharmacotherapy for SPD.	
 Change in Personality pathology: Total score at PID-5-BF Schizotypal Personality Disorder Diagnosis: Diagnosis at the 3rd module of SCID-5-PD interview; General Psychopathology: Total score at SCL-90-R; Metacognition: Total score at MAS-A 	9 measurements: (i) at 1 month before intervention starts; (ii) once the treatment starts; (iii) 6 measurements at the end of each month of intervention; at 1-month follow-up; Pre-post evaluation between pre-assessment (1-month before the intervention) and 1-month follow-up assessment.
Secondary Objectives To assess the safety of CMBT-S in patients diagnosed with SPD	
 Dropout rate Completion rate Adverse events (suicidal behaviors, self-harm, psychotic episodes) rate 	At the end of the intervention: dropout rate ($\leq 10\%$ of subjects), completion rate ($\leq 10\%$ of sessions skipped), adverse event rate ($\leq 10\%$ of subjects).

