7. TRIAL DESIGN

Randomized Controlled Trial with Repeated Measures.

After being informed about the study and potential risks, all patients giving written informed consent will undergo a psychological assessment so as to determine eligibility for study entry. Patients who meet the eligibility requirements will be randomized in a double-blind manner in a 1:1 ratio to new integrative

psychotherapy or treatment as usual (cognitive behavioral therapy plus standard psychopharmacological treatment). One month after the conclusion of the two forms of treatment (both lasting 6 months), patients will have access to the final follow-up assessment.

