12. STATISTICS

12.1. Statistical Analysis Plan (SAP)

Primary outcomes will be evaluated through repeated measures ANOVA. Statistical analyses and reporting will be conducted following CONSORT guidelines, with the primary analyses based on the ITT principle, which considered data from all participants whose baseline data were available. Multiple imputation will be adopted to estimate mid-assessment, post-treatment, and follow-up scores for noncompleters (e.g., those who had missed plus than 10% of sessions, or those who decline to participate in the TAU condition). Additionally, we will also conduct per-protocol (PP) analyses, which refers to inclusion in the analysis of only those patients who strictly adhered to the protocol.

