12.2. Sample Size Determination

ANOVA: Repeated measures, within-between interaction has been conducted in order to a priori compute required sample size. As input we estimate ([name], 2020) an effect size f equal to 0.37 with a power $(1-\beta)$ equal to 0.95. Moreover, we considered 9 measurements with at least a correlation among them equal to 0.50 (PID-5-BF reports a test-retest value greater than 0.70). This led to a total sample equal to 12 (critical $F= 2.0563726$; actual power= 0.9785743). By considering at least 10% of withdrawal we

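### The title claims non-inferiority, but the visible plan sets no margin or decision rule and powers only a test of difference, so a non-significant result could not support the claim

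*Combined protocol and SAP*

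**What the plan says.** The synopsis title is the only place in the visible text where non-inferiority appears: "A Pilot Non-inferiority Randomized Controlled Trial on Repeated Measures". The design row of the same synopsis says "Parallel Assignment Randomized Controlled Trial with Repeated Measures", and Section 7 says "Randomized Controlled Trial with Repeated Measures". Neither mentions non-inferiority.

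The primary objective in Section 6 is "To compare the effect of the CMBT-S versus CBT plus standard psychopharmacotherapy for SPD", which is neutral about the type of hypothesis. Section 12.1 states: "Primary outcomes will be evaluated through repeated measures ANOVA". It makes intention-to-treat the basis of the primary analyses and continues: "Additionally, we will also conduct per-protocol (PP) analyses". Neither analysis set is tied to a margin or an interval.

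Section 12.2 bases the sample size on an interaction test: "ANOVA: Repeated measures, within-between interaction has been conducted in order to a priori compute required sample size". Its inputs are f = 0.37, target power 0.95, nine measurements and a correlation of at least 0.50. It arrives at 12 patients, and the synopsis plans 14. The 10% limits in Section 6 concern dropout, skipped sessions and adverse events. They are not an efficacy margin.

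**The concern.** A non-inferiority conclusion needs three things fixed in advance: a margin, the contrast it applies to, and a rule that the confidence interval must exclude the margin. None is visible. The one test that the plan powers has a null hypothesis of no difference in time course between the arms. Failing to reject that null bounds nothing, and an omnibus F on 8 degrees of freedom has no direction to set against a margin.

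The gap therefore lies in the non-significant case. The comparator is CBT plus standard pharmacological treatment. A null result published under this title invites the reading that the new therapy is no worse than that package, and the visible text contains nothing to prevent it. A margin chosen after the data are seen would not be credible.

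**Working it through.** **1. The plan's own figure.** Inputs from Section 12.2: f = 0.37, m = 9 measurements, correlation ρ = 0.50, two arms. Alpha is not stated, but the critical F implies 0.05.

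λ = f²·N·m/(1 − ρ) = 0.1369 × 12 × 9 / 0.5 = 29.57, with df 8 and 8 × (12 − 2) = 80. The critical F is 2.05637 and the power 0.97857. Both match the plan. For 10% withdrawal, 12/0.9 = 13.3, which rounds up to 14 and matches the synopsis. The arithmetic is right, and it concerns detecting a difference.

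**2. What f = 0.37 means.** For a between-arm difference D (in SD) at follow-up, f = (D/2) × SD of the time profile. Three profiles are assumed, each scaled to reach 1 at follow-up: linear over the nine visits (SD 0.323), diverging from treatment start (0.346), and an immediate step after the two pre-treatment visits (0.416). Then f = 0.37 corresponds to D = 0.74/SD, or 2.3, 2.1 and 1.8 SD. The stated power is for a very large difference.

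**3. How often a worse therapy gives a null.** Take D = 0.5 SD worse. Example: linear, N = 12, ρ = 0.5 gives f = 0.25 × 0.323 = 0.0807, λ = 0.00651 × 108 / 0.5 = 1.41, and non-significance in 90%. At the other end, step, N = 14, ρ = 0.85 gives f = 0.1039, λ = 0.0108 × 126 / 0.15 = 9.07, and 50%.

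Non-significant trials, N = 12 / N = 14:

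| Profile | ρ = 0.5 | ρ = 0.7 | ρ = 0.85 |
|---|---|---|---|
| Linear | 90 / 89% | 86 / 84% | 75 / 70% |
| From start | 89 / 88% | 85 / 82% | 71 / 65% |
| Step | 86 / 84% | 79 / 75% | 58 / 50% |

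Section 12.2 gives the correlation as at least 0.50 and test-retest as above 0.70, so 0.70 is not a ceiling.

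**4. What the interval would say in those null trials.** The same profiles, N and ρ were simulated under compound symmetry with 10,000 trials per cell, using the mean of the two pre-treatment scores as covariate where adjusted. The table gives the share of non-significant trials whose 95% CI still includes more than the stated disadvantage.

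| Contrast | Beyond 0.5 SD worse | Beyond 1 SD worse |
|---|---|---|
| Follow-up, unadjusted | about 97–98% | about 85–89% |
| Follow-up, baseline-adjusted | about 96% or more | about 46–85% |
| Average of seven later visits, baseline-adjusted | about 73–97% | about 1–65% |

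In the two gradual profiles the average targets a difference smaller than 0.5 SD, which explains part of its lower figures.

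**5. Could 14 patients show non-inferiority?** Assume a true difference of 0, one-sided 2.5%, n = 7 per arm, and a noncentral t with SE = √(2v/n). The variance v is 1 for unadjusted follow-up, 1 − ρ² for baseline-adjusted follow-up, and (1 + 6ρ)/7 − ρ²/((1 + ρ)/2) for the average of seven later visits adjusted for two baselines. Power over ρ = 0.5 to 0.85:

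| Assumed margin | Unadjusted follow-up | Adjusted follow-up | Adjusted average |
|---|---|---|---|
| 0.5 SD | 14% | 17–37% | 42–81% |
| 1.0 SD | 41% | 50–90% | 94% to over 99% |

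With 12 evaluable patients, the 0.5 SD range across contrasts falls from 14–81% to 12–73%.

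**The case against.** The strongest reply is that this is a pilot, that Section 2 gives its purpose as assessing safety and efficacy, and that one word in a title does no harm if nobody acts on it. No passage says that a null result will be read as non-inferior, and the planned analysis can run unchanged. That stands: the harm is conditional. But the pilot label supplies no margin, and a power target of 0.95 shows that an inferential result is intended.

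The plan is also visible only in part. Some passages were removed, and Section 12.2 breaks off mid-sentence. The broken sentence concerns withdrawal, but what followed cannot be seen, so the point is limited to the visible text.

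A reader might infer more than the documents support:

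- That 14 patients are too few. This cannot be said, because power runs from 14% to over 99% depending on the assumed margin, contrast and correlation.
- That objective, analysis and sample size each contradict the title. The objective is neutral, and Section 12.1 does not say which ANOVA term decides. The mismatch rests mainly on Section 12.2 and the missing margin.
- That a null result would nearly always leave a disadvantage beyond 1 SD open. That holds for the unadjusted follow-up contrast, the least precise of the three, and not in general.
- That a null is the expected outcome if the therapy is 0.5 SD worse. The range reaches down to 50%.
- That the ANOVA is uninformative. A significant interaction, read with the arm means, would be informative.

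**Conclusion.** The point holds in this form: the plan names a design property that it does not deliver. Followed as written, it cannot support a non-inferiority conclusion, because the visible text has no margin, hypothesis or interval rule and its only powered test is one of difference. This part needs no assumptions.

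The sizes do rest on assumptions. With compound symmetry, three assumed time profiles and ρ between 0.5 and 0.85, a therapy 0.5 SD worse would give a non-significant interaction in 50% to 90% of trials. In most of those, the 95% CI would still include more than 0.5 SD worse, whichever of the three contrasts is used. The sample-size arithmetic is correct and is not at issue. The adequacy of 14 patients for non-inferiority remains undetermined.

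**What to change.** **Recommended.** Remove Non-inferiority from the title. Add to Section 12.1: *A non-significant group-by-time interaction will not be interpreted as non-inferiority or equivalence.* Beside the ANOVA, report the between-arm PID-5-BF difference with its 95% CI, at a named timepoint or for a named average of later visits. The ANOVA and the sample size stay.

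**If the label is kept.** Before analysis, pre-specify a justified PID-5-BF margin, the contrast it applies to and a 95% CI rule, and state that the power in Section 12.2 does not apply to that test. Fourteen patients may or may not then be enough.

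**Cost.** The recommended route needs wording changes and one extra estimate, and gives up the non-inferiority label. It adds no patients or visits. The synopsis lists the trial as recruiting, and Section 16.3 requires substantial amendments to be submitted and, where necessary, approved, so an amendment submission may be needed.

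The synopsis names PID-5-BF as the only primary outcome, whereas Section 6 lists four measures under the primary objective. That is a separate matter and should be raised on its own.

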4. ABBREVIATIONS

AE	Adverse event
AR	Adverse reaction

CBT	Cognitive Behavioral Therapy
CFT	Compassion Focused Therapy
CMBT-S	Compassion and Metacognition Based Treatment for Schizotypal Personality Disorder
CI	Chief Investigator
CRA	Clinical Research Associate (Monitor)
CRF	Case Report Form
CRO	Contract Research Organisation
CT	Clinical Trials
CTA	Clinical Trials Authorisation
CTRG	Clinical Trials and Research Governance
DMC/DMSC	Data Monitoring Committee / Data Monitoring and Safety Committee
DSUR	Development Safety Update Report
GCP	Good Clinical Practice
GP	General Practitioner
GTAC	Gene Therapy Advisory Committee
HRA	Health Research Authority
IB	Investigators Brochure
ICF	Informed Consent Form
ICH	International Conference on Harmonisation
IMP	Investigational Medicinal Product
IRB	Independent Review Board
MERIT	Metacognitive Reflection and Insight Therapy
MIT	Metacognitive Interpersonal Therapy
MHRA	Medicines and Healthcare products Regulatory Agency
NHS	National Health Service
RES	Research Ethics Service
OXTREC	Oxford Tropical Research Ethics Committee
PI	Principal Investigator
PID-5-BF	Personality Inventory for DSM-5,Brief Form
PIL	Participant/ Patient Information Leaflet
R&D	NHS Trust R&D Department
REC	Research Ethics Committee
RSI	Reference Safety Information
SAE	Serious Adverse Event

SAR	Serious Adverse Reaction
SCID-5-PD	Structured Clinical Interview for DSM-5 Personality Disorders
SCL-90-R	Symptom Checklist – 90 – Revised
SDV	Source Data Verification
SMPC	Summary of Medicinal Product Characteristics
SOP	Standard Operating Procedure
SPD	Schizotypal Personality Disorder
SUSAR	Suspected Unexpected Serious Adverse Reactions
TMF	Trial Master File
TSG	Oxford University Hospitals NHS Foundation Trust / University of Oxford Trials Safety Group

5. BACKGROUND AND RATIONALE

Schizotypal personality disorder (SPD) reflects a pervasive pattern of maladaptive behaviour, which has been suggested to involve either three or four different facets. These include positive features such as ideas of reference, magical thinking and suspiciousness; negative features such as anhedonia and lack of social interest; and cognitive features that involve disorganized thinking and impulsive nonconforming behaviour. SPD has been alternatively considered a personality disorder (PD), a subclinical form of schizophrenia or an expression of the liability for the development of schizophrenia. DSM-5 reports a prevalence of 4.6% in general population, with poor long-term outcomes, including significant impairments in social relationships, work and leisure activities, and a typical declining trajectory in overall functioning. Treatment options are scarce, and a systematic review published in 2018, reported just three psychosocial interventions for SPD. In the last three years, I acted as Principal Investigators of four studies aimed at outlining a novel, evidence-based intervention tailored for SPD. The general aim was to test an integrative psychotherapy rooted in metacognitively oriented psychotherapies and compassion focused therapy. A growing body of research suggests that many diagnosed with personality disorders and psychosis experience deficits in metacognition or the ability to form integrated ideas about themselves and others. They also struggle to regulate their brain's evolved systems for decoding and responding to communication signals, and report a recurrent inability to regulate their arousal when facing internal (e.g. shame) and external (e.g. relations) stimuli. Since SPD is a severe mental illness at the crossroads between personality disorder and psychosis, my colleagues and I suggest considering it from these deficits in metacognition and socially evolved systems. We tested how metacognition may be a primary target of a tailored psychotherapy. And we are recently exploring the role of compassion for one's own distress, as a way to strengthen the ability to generate a self-soothing response to suffering. First, together with [name] (Indiana University, Indianapolis) and [name] (Center for Metacognitive Intepersonal Therapy, Rome) [name] (Tages Onlus) outlined and delivered a pilot study to test the suitability of a metacognitively oriented intervention for patients diagnosed with SPD ([name], Lysaker, Dimaggio, 2019). Second, we tested a specifically designed assessment strategy for SPD integrating measures of metacognition, big five, alternative model of personality disorders ([name], 2020)). Third, together with [name] (John Cabot University, Rome) and [name] (Tages Onlus, Florence) we explored the suitability of online compassion focused therapy interventions for clients with recent early psychotic episodes ([name], [name], Petrocchi, 2020). Four, we recently concluded a study on a large sample of non-clinical young adults (n=2234), aimed at exploring the moderating role of self-soothing and metacognition in the onset of a SPD. All these studies are seemingly supporting the need for a novel, integrative treatment for SPD, that is going to be test in randomized clinical trial.

In conclusion, the collected, even if partial, evidences and my clinical experience in treating SPD, may represent an opportunity for participants to better understand how to outline a treatment plan for an understudied area of psychopathology.

6. OBJECTIVES AND OUTCOME MEASURES

Objectives	Outcome Measures	Timepoint(s) of evaluation of this outcome measure (if applicable)
Primary Objective To compare the effect of the CMBT-S versus CBT plus standard psychopharmacotherapy for SPD.	
 Change in Personality pathology: Total score at PID-5-BF Schizotypal Personality Disorder Diagnosis: Diagnosis at the 3rd module of SCID-5-PD interview; General Psychopathology: Total score at SCL-90-R; Metacognition: Total score at MAS-A 	9 measurements: (i) at 1 month before intervention starts; (ii) once the treatment starts; (iii) 6 measurements at the end of each month of intervention; at 1-month follow-up; Pre-post evaluation between pre-assessment (1-month before the intervention) and 1-month follow-up assessment.
Secondary Objectives To assess the safety of CMBT-S in patients diagnosed with SPD	
 Dropout rate Completion rate Adverse events (suicidal behaviors, self-harm, psychotic episodes) rate 	At the end of the intervention: dropout rate ($\leq 10\%$ of subjects), completion rate ($\leq 10\%$ of sessions skipped), adverse event rate ($\leq 10\%$ of subjects).

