8.2. Inclusion Criteria

- Participant is willing and able to give informed consent for participation in the trial.
- Male or Female, aged 18 years or above.
- Diagnosed with Schizotypal Personality Disorder at SCID-5-AMPD.

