16.3. Approvals

Following Sponsor approval the protocol, informed consent form, participant information sheet will be submitted to an appropriate Research Ethics Committee (REC), HRA (where required), regulatory authorities (MHRA in the UK), and host institution(s) for written approval.

The Investigator will submit and, where necessary, obtain approval from the above parties for all substantial amendments to the original approved documents.

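### The synopsis names PID-5-BF as the only primary outcome, but section 6 lists four unranked measures under the Primary Objective and section 12.1 does not say which primary outcomes it tests

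*Combined protocol and SAP*

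**What the plan says.** The plan describes its outcomes in four places.

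- **Section 3, Synopsis.** The primary row has one entry, "Personality pathology: Total score at PID-5-BF", measured at nine time points. The secondary row reads "Schizotypal Personality Disorder Diagnosis: Diagnosis at the 3rd module of SCID-5-PD interview; General Psychopathology: Total score at SCL-90-R; Metacognition: Total score at MAS-A", evaluated pre-post.
- **Section 6, Objectives and Outcome Measures.** The Primary Objective row contains all four measures, beginning "Change in Personality pathology: Total score at PID-5-BF Schizotypal Personality Disorder Diagnosis: Diagnosis at the 3rd module of SCID-5-PD interview". The time-point cell gives the nine-measurement schedule first and then "Pre-post evaluation between pre-assessment (1-month before the intervention) and 1-month follow-up assessment". The secondary row covers safety only: dropout, completion and adverse event rates.
- **Section 12.1, SAP.** "Primary outcomes will be evaluated through repeated measures ANOVA". No outcome is named. The section adds rules for ITT, multiple imputation and per-protocol analysis.
- **Section 12.2, Sample Size Determination.** "Moreover, we considered 9 measurements with at least a correlation among them equal to 0.50 (PID-5-BF reports a test-retest value greater than 0.70". PID-5-BF is the only instrument mentioned. The available text of this section breaks off in mid-sentence.

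**The concern.** The two outcome tables disagree in both rows. The synopsis has one primary efficacy measure and section 6 has four. The synopsis secondary row holds three efficacy measures and no safety rates, while the section 6 secondary row holds safety rates and no efficacy measures. Section 12.1 does not settle the matter, because it uses a plural and names nothing.

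The reading chosen changes what the trial tests. Under the synopsis, one test carries the primary claim, and the other three measures have a pre-post comparison but no named method. Under section 6 with section 12.1, four tests serve the primary objective without adjustment, and one of them is an ANOVA on a yes/no diagnosis recorded at two time points. No efficacy success rule is stated; the only thresholds, in section 6, are for dropout, completion and adverse events. In a trial of 14 people that plans a comparative test, the outcome behind the main claim should be fixed in the analysis section itself.

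**Working it through.** **1. Which reading does the sample size support?**

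Inputs from section 12.2: f = 0.37, m = 9 measurements, correlation ρ = 0.50, N = 12, critical F = 2.0563726, actual power = 0.9785743. There are k = 2 groups (section 7, 1:1 allocation). Alpha is not given in the available text.

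- df1 = (k − 1)(m − 1) = 8; df2 = (N − k)(m − 1) = 10 × 8 = 80.
- The 95th percentile of F(8, 80) is 2.0563726, which matches the plan. The implied alpha is therefore 0.05, for one test.
- λ = N·m·f²/(1 − ρ) = 12 × 9 × 0.1369/0.50 = 29.57.
- Power from the noncentral F = 0.9785743, which matches the plan. N = 10 gives 0.941, below the 0.95 target, so 12 is the smallest even N that meets it.
- Allowing 10% withdrawal, 12/0.90 = 13.3, which rounds up to 14 as in the synopsis.

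Only PID-5-BF is measured nine times. The calculation therefore sizes one test of PID-5-BF at 0.05, in line with the synopsis.

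**2. The outcome tables side by side**

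| Measure | Synopsis | Section 6 | Time points | Method in 12.1 |
|---|---|---|---|---|
| PID-5-BF total | Primary | Primary Objective | 9 | ANOVA, if primary |
| SCID-5-PD diagnosis | Secondary | Primary Objective | 2 | ANOVA if primary; otherwise none named |
| SCL-90-R total | Secondary | Primary Objective | 2 | Same |
| MAS-A total | Secondary | Primary Objective | 2 | Same |
| Dropout, completion, adverse events | Not listed | Secondary | End of intervention | None named |

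**3. What would four primary tests cost?**

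Assumption: any one of four two-sided tests at 0.05 counts as efficacy success. The documents neither state nor exclude this rule.

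- Independent tests: 1 − 0.95⁴ = 0.1855.
- Correlated tests: four normal test statistics with common correlation r, by numerical integration. The correlations are assumed, since the documents give none between measures.

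| r | 0 | 0.3 | 0.5 | 0.7 | 0.9 |
|---|---|---|---|---|---|
| P(at least one false positive) | 0.185 | 0.174 | 0.156 | 0.130 | 0.094 |

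The comparison value is 0.05 for a single test. These are illustrative z-tests and not the planned F tests.

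**The case against.** The strongest reply is that the intended primary outcome is not really in doubt. The synopsis is the only place that ranks outcomes, and it is explicit. Section 6 ranks objectives (efficacy, then safety), and one objective may hold several measures. Its time-point cell keeps the synopsis's split between nine measurements and pre-post. The sample size names PID-5-BF alone. All of this stands, and it limits how serious the point is. It does not remove the point: separate timing is not a rank, and section 12.1 still names no outcome. The plural in 12.1 is only weak evidence for four primaries, since the document's wording is loose elsewhere.

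A reader might draw four stronger conclusions that the documents do not support.

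- **The trial's false-positive rate is 18.5%.** This needs the any-one-of-four rule, which is stated nowhere, and independent tests.
- **Nothing stops the primary outcome being chosen after the data are seen.** The synopsis does restrain this, because a switch would contradict its primary row. The gap is in sections 6 and 12.1.
- **ANOVA on the diagnosis is a demonstrated error.** With 7 per arm, all assumed positive at pre-assessment, ANOVA and Fisher's exact test disagree at 0.05 in 8 of 64 possible tables, for example 4 against 0 losing the diagnosis (p = 0.015 and 0.070). The maximum size is 5.7% for ANOVA and 1.3% for Fisher, so the gap mainly reflects Fisher's conservatism. A method for proportions suits a yes/no outcome better, but serious error inflation is not shown.
- **The trial is too small for the other three measures.** It was not sized on them, and sizing on one primary outcome is not a fault.

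Finally, section 12.2 breaks off, so a statement of alpha or of further analyses may be lost. Saying that the plan has no analysis for the secondary measures would go too far; the available text names no test for them.

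**Conclusion.** The inconsistency is real and can be read directly from the text: one primary outcome in the synopsis, four unranked measures under the Primary Objective in section 6, and unnamed plural primary outcomes in section 12.1. The synopsis and the sample size together make PID-5-BF the evident intention, so this is a failure to state the primary outcome where the analysis is specified, and not a trial without one.

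The possible cost is a false-positive rate of about 9% to 18.5% in place of 5%. That range rests on three assumptions: section 6 is followed, any one of four tests at 0.05 counts as success, and the correlation between tests lies between 0 and 0.9. Alpha of 0.05 is inferred from the plan's critical F. The textual contradiction holds without these figures.

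This should be fixed. The planned N, the data collection and the powered test all stand.

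**What to change.** 1. In sections 6 and 12.1, name PID-5-BF total score over the nine measurements as the single primary outcome and its test as the only one supporting the primary claim. Keep N at 14.
2. List SCID-5-PD diagnosis, SCL-90-R and MAS-A as secondary, reported as between-arm estimates with 95% confidence intervals and no confirmatory claim. Use a method for proportions for the diagnosis. For the two scales, use the pre-assessment and follow-up scores already collected.
3. Make the secondary rows of the synopsis and section 6 agree, with dropout, completion and adverse event rates in both.
4. Make the change, and record its date, before outcome data are examined.

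**Cost.** These are text changes only, with no new data and no change in N. The synopsis lists the trial as recruiting, and section 16.3 says "The Investigator will submit and, where necessary, obtain approval from the above parties for all substantial amendments to the original approved documents", so approval may be needed. The sponsor also gives something up: a positive result on diagnosis, SCL-90-R or MAS-A could not be presented as primary.

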9.4. Randomisation

A simple computer will generate random number for each participant. CRO will design the randomization schedule and will hold the allocation blind to all the investigators.

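### The only schizotypal-specific efficacy outcome is listed as diagnosis present or absent; with about 7 per arm a graded criterion count, if the interview yields one, would separate the arms better

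*Combined protocol and SAP*

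**What the plan says.** Section 6 (Objectives and Outcome Measures) lists "Schizotypal Personality Disorder Diagnosis: Diagnosis at the 3rd module of SCID-5-PD interview", assessed at pre-assessment and at 1-month follow-up. PID-5-BF, SCL-90-R and MAS-A are each listed as a total score; this outcome alone names no score. The synopsis lists it as secondary, while section 6 places it under the primary objective.

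Entry rests on a differently named instrument. Section 8.2 requires "Diagnosed with Schizotypal Personality Disorder at SCID-5-AMPD".

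The synopsis gives "Sample Size 14". Section 12.2 derives that size for PID-5-BF: "This led to a total sample equal to 12", before an allowance for withdrawal. Section 7 plans a 1:1 ratio and section 9.4 says only that "A simple computer will generate random number for each participant". Section 12.1 names repeated measures ANOVA for primary outcomes. No test, margin or expected rate is given for the diagnosis outcome.

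**The concern.** The other efficacy outcomes cover personality pathology, general psychopathology and metacognition. This is the only one specific to the disorder being treated, and it comes from an interview rather than a questionnaire.

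A yes/no result loses information around the threshold. A patient just above it becomes a success by losing one criterion. A patient far above it can lose several and still count as unchanged. With about seven per arm, and no stratification described, chance imbalance in how far patients start above the threshold can create or hide a difference in remission.

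The two instruments add a second problem. A patient admitted on SCID-5-AMPD but negative on SCID-5-PD at pre-assessment cannot lose the diagnosis, and the plan does not say how such a patient is counted.

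**Working it through.** **1. The plan's own figure.** Section 12.2 uses "an effect size f equal to 0.37 with a power" of 0.95, and "we considered 9 measurements with at least a correlation among them equal to 0.50". For the within-between interaction with N=12, two groups and 9 measurements:
- noncentrality = f²·N·m/(1−ρ) = 0.37² × 12 × 9 / 0.50 = 29.57
- degrees of freedom 8 and (12−2)×8 = 80
- critical F = 2.0564 at alpha 0.05, power = 0.9786

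Both match the plan. 12/0.9 = 13.3, rounded up to 14. This power belongs to PID-5-BF and does not carry over to a yes/no outcome.

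**2. Smallest detectable difference, yes/no.** The plan names no test, so two-sided Fisher at 0.05 is my assumption. At 7 v 7:
- 0 v 5: 2·C(7,5)/C(14,5) = 42/2002 = 0.021
- 1 v 6: 2·(49+1)/3432 = 0.029
- 0 v 4: 2·C(7,4)/C(14,4) = 70/1001 = 0.070
- 1 v 5: 2·(147+7)/3003 = 0.103

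So five patients are needed. The same holds at 6 v 6 (0 v 5 p=0.015; 0 v 4 p=0.061). Section 9.4 describes no blocking; under independent 50:50 allocation the chance of an exact 7:7 split is 3432/16384 = 0.21. At 6:8, 1 v 6 gives p=0.103, so even some five-patient differences miss.

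Boschloo's test gives 0 v 4 p=0.024, so four can suffice. It does so only when one arm is all or none: for 1 v 5, with the tied table 2 v 6 included, the p-value is 2×470/16384 = 0.057.

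**3. Yes/no against a count.** Assumptions not in the documents: 9 criteria, threshold 5, all patients at or above threshold at baseline, baseline counts 5 to 9 with probabilities 0.30, 0.30, 0.20, 0.12, 0.08, no new criteria and no rating error. Each baseline criterion is lost with a fixed probability.

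At loss probability 0.2 and no within-patient correlation, the chance of falling below 5 is 0.672, 0.345, 0.148, 0.056 and 0.020 for starting counts of 5 to 9. The weighted rate is 0.202+0.103+0.030+0.007+0.002 = 0.343. At loss probability 0.5 the same sum gives 0.829. Summing binomial probabilities over the significant 7 v 7 tables gives the yes/no powers below. Count power is from simulation, using analysis of covariance on the follow-up count adjusted for the baseline count. Correlated loss is beta-binomial.

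| Loss probabilities | Within-patient correlation | Yes/no, Fisher | Yes/no, Boschloo | Adjusted count |
|---|---|---|---|---|
| 0.5 v 0.2 | 0 | 26% | 33% | 75% |
| 0.5 v 0.2 | 0.2 | 17% | 21% | 46–47% |
| 0.5 v 0.2 | 0.4 | 14% | 17% | 33–35% |
| 0.4 v 0.2 | 0 | 12% | 15% | 45–46% |
| 0.4 v 0.2 | 0.2 | 8% | 11% | 25% |
| 0.4 v 0.2 | 0.4 | 6% | 9% | 18% |

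Simulating the Fisher column at zero correlation gave 25–27% and 10–12%, in line with the enumeration. Under the null (0.2 v 0.2) Fisher rejects about 1% of the time and the count about 5%. For 0.5 v 0.2 with no correlation, 6 per arm gives 14% v 68%, and flat baseline counts give 29% v 80%.

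**4. A second model.** With a latent normal score at 7 v 7, a shift of 1.5 SD gives 73% power for the score and 16–35% for yes/no by Fisher (remission in the worse arm 10–50%). At 1.0 SD the figures are 41% and 5–15%. The score needs about 1.63 SD for 80% power.

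**The case against.** - **The count may not exist.** The documents do not describe how SCID-5-PD is scored, and no case report form is shown. A reader might infer that criterion ratings are made and then discarded. The documents say only that no such score is listed as an outcome. This stands: the proposal is conditional on the interview rating each criterion.
- **The outcome is not simply remission.** A reader might infer that everyone starts positive because the diagnosis is an entry criterion. Entry uses SCID-5-AMPD and the outcome uses SCID-5-PD, so this is not established. It also means that the simulated baselines, all at or above threshold, model a condition the protocol does not impose.
- **Five patients depends on the test.** This stands; the plan names none and Boschloo's test can do with four. But Boschloo raises yes/no power only to 33% and 15% in the uncorrelated scenarios, still well below the count.
- **The power contrast can be overstated.** The 26% v 75% contrast assumes criteria are lost independently within a patient and compares a conservative test with one near its nominal level. This stands, which is why the range is shown. The count ranked higher in every non-null scenario.
- **Significance is a weak yardstick.** The title calls this a pilot non-inferiority trial, the synopsis lists the outcome as secondary, and remission is easy to read clinically. These are fair reasons to keep reporting remission, but not to omit a graded result.

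**Conclusion.** The point holds in a limited form. As listed, the only schizotypal-specific efficacy outcome is present/absent. At 7 per arm it needs a five-patient difference by two-sided Fisher, or four in the extreme tables by Boschloo. Its baseline status is not fixed by the entry criterion. If the interview yields a criterion count, analysing it with baseline adjustment raises power by a factor of roughly two to four over Fisher under the assumed 9/5 structure and loss rates. The larger gains need criteria to be lost nearly independently.

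A reader might go further and conclude that a count would make this outcome adequately powered. It would not: in no tabulated scenario at 7 per arm does it reach 80%, and the sample size was set for PID-5-BF. The gain is a more informative estimate, with its spread, from the same interview.

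**What to change.** In the synopsis and section 6, define this outcome as the number of SCID-5-PD schizotypal criteria rated present at 1-month follow-up, compared between arms with adjustment for the number at pre-assessment. First confirm that the interview is scored criterion by criterion. Report loss of the diagnosis descriptively by arm, among patients SCID-5-PD positive at pre-assessment, and state how many were negative then. Name the analysis in section 12.1, and give the outcome the same status (primary or secondary) in both places.

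The cost is outcome wording and, if not already captured, one more case report form variable at each of the two assessments; no extra visits, interviews or patients are needed. A count is less familiar to clinicians than remission, which is why remission is still reported, and the comparison remains imprecise with 14 patients.
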